#### **4.4 Concomitant Medications/Treatments**

Patients should not be receiving any treatment for prostate cancer, including anti androgen therapy as this can affect  $^{68}\text{Ga}$  PSMA-11 uptake.

#### **4.5 Other Modalities or Procedures**

The initial mp-MRI of the prostate is standard of care and not part of the research protocol. Per current guidelines [18], cross sectional imaging (CT or MRI) is also considered standard of care in men with unfavorable intermediate or high risk disease.

#### **4.6 Duration of Follow Up**

2 years

#### **4.7 Removal of Subjects from Protocol**

Subjects will be removed from therapy when any of the criteria listed in [Section 5.5](#) apply. Notify the Principal Investigator, and document the reason for treatment discontinuation and the date of discontinuation. The subject should be followed-up per protocol.

#### **4.8 Subject Replacement**

If a subject is removed from the study for any reason, he may be replaced.

### **5.0 STUDY PROCEDURES**

#### **5.1 Screening/Baseline Procedures**

Assessments performed exclusively to determine eligibility for this study will be done only after obtaining informed consent. Assessments performed for clinical indications (not exclusively to determine study eligibility) may be used for baseline values even if the studies were done before informed consent was obtained.

---

All screening procedures must be performed within 3 months prior to registration unless otherwise stated. The screening procedures include:

**5.1.1 *Informed Consent***

Informed consent will be obtained from each research participant by the investigator or the study coordinator. No participant will be allowed to participate without a signed, IRB consent form

**5.1.2 *Medical history***

Review of complete medical and surgical history up to 60 days available in the electronic medical record system at UT Southwestern Medical Center

**5.1.3 *Demographics***

Age, gender, race, ethnicity

**5.1.4 *Review subject eligibility criteria***

**5.1.5 *Review previous and concomitant medications***

**5.1.6 *Physical exam including vital signs, height and weight***

Vital signs (temperature, pulse, respirations, blood pressure), height, weight

**5.1.7 *Adverse event assessment***

Baseline adverse events will be assessed. See section 7 for Adverse Event monitoring and reporting.

**5.1.8 *Blood draw for correlative studies***

N/A

**5.1.9 *Serum chemistries***

None is needed for  $^{68}\text{Ga}$  PSMA-11 PET/CT.

**5.2 *Procedures During Treatment***

There is no planned treatment. The subjects will come to PET/CT imaging suite and an intravenous catheter will be placed. The subject will have height and weight measured in order to calculate dose of  $^{68}\text{Ga}$  PSMA-11 to be injected.

**5.3 *Follow-up Procedures***

Follow-up of patient's clinical condition, pathology, laboratory values and imaging studies related to the study disease will occur for 2 years to correlate with the imaging results. Adverse events will be evaluated up to 24 hours. Due to the drug's short half-life of 68 min and the toxicological profile, no long-term toxicities are anticipated.

#### 5.4 Time and Events Table

Event	Visit 1: screening	Visit 2:  GA PSMA-11 PET/CT	Follow-up
Informed Consent	X		
Demographics	X		
Clinical history	X		
Height/weight	X	X	
Physical exam	X		
Survival/patient status			X
Review pathology records			X
 Ga PSMA-11 PET/CT		X	
Other radiologic studies (CT or MRI)	X		X
Adverse event evaluation*			X

\*Adverse event evaluation up to 24 hours post injection.

#### 5.5 Removal of Subjects from Study

Subjects may withdraw from the study at any time at their own request, or they may be withdrawn at the discretion of the investigator for safety, behavioral or administrative reasons. The reason(s) for discontinuation will be documented and may include:

- 5.5.1 Subject voluntarily withdraws from treatment (follow-up permitted);
- 5.5.2 Subject withdraws consent (termination of treatment and follow-up);
- 5.5.3 Subject is unable to comply with protocol requirements;
- 5.5.4 Subject experiences toxicity that makes continuation in the protocol unsafe;
- 5.5.6 Treating physician determines that continuation on the study would not be in the subject's best interest;
- 5.5.7 Subject becomes pregnant (pregnancy to be reported along same timelines as a serious adverse event);
- 5.5.9 Lost to follow-up. If a research subject cannot be located to document disease state after a period of 2 years, the subject may be considered "lost to follow-up". All attempts to contact the subject during the two years must be documented and approved by the Data Monitoring Committee.

#### 6.0 Measurement of Effect

This is a non-therapeutic, exploratory protocol. The protocol focuses on exploring the ability of GA PSMA-11 to demonstrate primary and metastatic disease in patients with suspected prostate cancer.

---

## 6.1 Safety/tolerability

As with all PET/CT imaging agents, Ga PSMA-11 is a radiopharmaceutical that decays with positron emission, a form of radiation. This poses a radiation risk but this risk is extremely small at the dose administered in this study. The organ and total body doses associated with Ga PSMA-11 are comparable to or lower than those associated with other widely used clinical nuclear medicine procedures.

The radiation absorbed effective dose from the intravenously injected Ga PSMA-11 is estimated to be 237 mRem (2.37mSv) [19].

Risks of PET/CT studies include those due to IV line placement. These risks include bleeding or possible hematoma at the site of the injection. A physician will be available to document the adequacy of the venous line and to provide assistance in case of inadvertent tracer extravasations or hematoma formation.

All adverse events occurring within a 24 hour period post Ga PSMA-11 infusion will be recorded. The adverse events to be specifically monitored during the infusion include localized discomfort at the IV injection site, pain, respiratory difficulties, flushing, dizziness, pruritus/rash, and any other symptoms that could be secondary to an anaphylactic reaction. The subject will be instructed to report any subjective symptoms or sensory changes noted.

## 7.0 ADVERSE EVENTS

### 7.1 Experimental Therapy

There is no experimental therapy. This is an imaging only study.

### 7.1 Adverse Event Monitoring

Adverse event data collection and reporting, which are required as part of every clinical trial, are done to ensure the safety of subjects enrolled in the studies as well as those who will enroll in future studies. Adverse events are reported in a routine manner at scheduled times during a trial. Additionally, certain adverse events must be reported in an expedited manner to allow for optimal monitoring of subject safety and care.

All subjects experiencing an adverse event, regardless of its relationship to study therapy, will be monitored until:

- the adverse event resolves or the symptoms or signs that constitute the adverse event return to baseline or is stable in the opinion of the investigator;
- there is a satisfactory explanation other than the study therapy for the changes observed; or
- death.

#### 7.1.1 Definitions

An adverse event is defined as any untoward or unfavorable medical occurrence in a human research study participant, including any abnormal sign (for example, abnormal physical exam, imaging finding or clinically significant laboratory finding), symptom, clinical event, or disease, temporarily associated with the subject's participation in the research, whether or not it is considered related to the subject's participation in the research.

Adverse events encompass clinical, physical and psychological harms. Adverse events occur most commonly in the context of biomedical research, although on occasion, they

---

can occur in the context of social and behavioral research. Adverse events may be expected or unexpected.

#### Acute Adverse Events

Adverse events occurring in the time period from the signing of the informed consent, through 24 hours post treatment will be considered acute adverse events.

#### Severity

Adverse events will be graded by a numerical score according to the defined NCI Common Terminology Criteria for Adverse Events (NCI CTCAE) Version 5.0. Adverse events not specifically defined in the NCI CTCAE will be scored on the Adverse Event log according to the general guidelines provided by the NCI CTCAE and as outlined below.

- Grade 1: Mild
- Grade 2: Moderate
- Grade 3: Severe or medically significant but not immediately life threatening
- Grade 4: Life threatening consequences
- Grade 5: Death related to the adverse event

#### Serious Adverse Events

ICH Guideline E2A and the UTSW IRB define serious adverse events as those events, occurring at any dose, which meets any of the following criteria:

- Results in death
- Immediately life-threatening
- Results in inpatient hospitalization or prolongation of existing hospitalization
- Results in persistent or significant disability/incapacity
- Results in a congenital anomaly/birth defect
- Based upon appropriate medical judgment, may jeopardize the subject's health and may require medical or surgical intervention to prevent one of the other outcomes listed in this definition.

Note: A “Serious adverse event” is by definition an event that meets **any** of the above criteria. Serious adverse events may or may not be related to the research project. A serious adverse event determination does not require the event to be related to the research. That is, both events completely unrelated to the condition under study and events that are expected in the context of the condition under study may be serious adverse events, independent of relatedness to the study itself. As examples, a car accident requiring  $>24$  hour inpatient admission to the hospital would be a serious adverse event for any research participant; likewise, in a study investigating end-stage cancer care, any hospitalization or death which occurs during the protocol-specified period of monitoring for adverse and serious adverse events would be a serious adverse event, even if the event observed is a primary clinical endpoint of the study.

Pre-planned hospitalizations or elective surgeries are not considered SAEs. Note: If events occur during a pre-planned hospitalization or surgery, that prolong the existing hospitalization, those events should be evaluated and/or reported as SAEs.

 NCI defines hospitalization for expedited AE reporting purposes as an inpatient hospital stay equal to or greater than 24 hours. Hospitalization is used as an indicator of the seriousness of the adverse event and should only be used for situations where the AE

---

truly fits this definition and NOT for hospitalizations associated with less serious events. For example: a hospital visit where a patient is admitted for observation or minor treatment (e.g. hydration) and released in less than 24 hours. Furthermore, hospitalization for pharmacokinetic sampling is not an AE and therefore is not to be reported either as a routine AE or in an expedited report.

**7.1.2 Unanticipated Problems Involving Risks to Subjects or Others (UPIRSOs):**

The phrase “unanticipated problems involving risks to subjects or others” is found, but not defined in the HHS regulations at 45 CFR 46, and the FDA regulations at 21 CFR 56.108(b)(1) and 21 CFR 312.66. For device studies, part 812 uses the term unanticipated adverse device effect, which is defined in 21 CFR 812.3(s). Guidance from the regulatory agencies considers unanticipated problems to include any incident, experience, or outcome that meets ALL three (3) of the following criteria:

- Unexpected in terms of nature, severity or frequency given (a) the research procedures that are described in the protocol-related documents, such as the IRB-approved research protocol and informed consent document; and (b) the characteristics of the subject population being studied;  
**AND**
- Related or possibly related to participation in the research (possibly related means there is a reasonable possibility that the incident, experience, or outcome may have been caused by the procedures involved in the research);  
**AND**
- Suggests that the research places subjects or others at greater risk of harm (including physical, psychological, economic, or social harm) than was previously known or recognized. Note: According to OHRP, if the adverse event is serious, it would always suggest a greater risk of harm.

**Follow-up**

All adverse events will be followed up according to good medical practices.

**7.2 Steps to Determine If a Serious Adverse Event Requires Expedited Reporting to the SCCC DSMC and/or HRPP**

Step 1: Identify the type of adverse event using the NCI Common Terminology Criteria for Adverse Events (CTCAE v5).

Step 2: Grade the adverse event using the NCI CTCAE v5.

Step 3: Determine whether the adverse event is related to the protocol therapy.

Attribution categories are as follows:

- Definite – The AE is *clearly related* to the study treatment.
- Probable – The AE is *likely related* to the study treatment.
- Possible – The AE *may be related* to the study treatment.
- Unlikely – The AE *may NOT be related* to the study treatment.
- Unrelated – The AE is *clearly NOT related* to the study treatment.

Note: This includes all events that occur within 24 hours of the last dose of protocol treatment. Any event that occurs more than 24 hours after the last dose of treatment and is attributed (possibly, probably, or definitely) to the agent(s) must also be reported as indicated in the sections below.

---

 Revised to 24 hours due to the drugs short half-life of 68 min.

**Step 4:** Determine the prior experience of the adverse event. Expected events are those that have been previously identified as resulting from administration of the treatment. An adverse event is considered unexpected, for expedited reporting purposes only, when either the type of event or the severity of the event is not listed in:

- the current known adverse events listed in the Agent Information Section of this protocol (if applicable);
- the drug package insert (if applicable);
- the current Investigator's Brochure (if applicable)
- the Study Agent(s)/Therapy(ies) Background and Associated Known Toxicities section of this protocol

#### **7.2.1 Reporting SAEs and UPIRSOs to the Simmons Comprehensive Cancer Center (SCCC) Data Safety Monitoring Committee (DSMC)**

All SAE/UPIRSOs at all sites, which occur in research subjects on protocols for which the SCCC is the DSMC of record require reporting to the DSMC regardless of whether IRB reporting is required. All SAEs/UPIRSOs occurring during the protocol-specified monitoring period should be submitted to the SCCC DSMC within 5 business days of the PI or delegated study team members awareness of the event(s). In addition, for participating centers other than UTSW, local IRB guidance should be followed for local reporting of serious adverse events.

The UTSW study team is responsible for submitting SAEs/UPIRSOs to the SCCC DSMC Coordinator. Hardcopies or electronic versions of the eIRB Reportable Event report; FDA Form #3500A forms, or other sponsor forms, if applicable; and/or any other supporting documentation available should be submitted to the DSMC Coordinator. The DSMC Coordinator forwards the information onto the DSMC Chairman who determines if immediate action is required. Follow-up eIRB reports, and all subsequent SAE/UPIRSO documentation that is available are also submitted to the DSMC Chair who determines if further action is required. (*See Appendix III of the SCCC DSMC Plan for a template Serious Adverse Event Form which may be utilized when a sponsor form is unavailable and SAE submission to the eIRB is not required.*)

If the event occurs on a multi-institutional clinical trial coordinated by the UTSW Simmons Comprehensive Cancer Center, the DOT Manager or lead coordinator ensures that all participating sites are notified of the event and resulting action, according to FDA guidance for expedited reporting. DSMC Chairperson reviews all SAEs/UPIRSOs upon receipt from the DSMC Coordinator. The DSMC Chairperson determines whether action is required and either takes action immediately, convenes a special DSMC session (physical or electronic), or defers the action until a regularly scheduled DSMC meeting.

**The following instructions section may be modified as needed to ensure clear guidance for institutions participating in the trial who will not report directly to the UTSW Institutional Review Board. If needed, this reporting may be facilitated by the UTSW study team for example.**

Telephone reports to: [name] MD, [contact] [contact]
--

### **Reporting Unanticipated Problems Involving Risks to Subjects or Others (UPIRSOs) to the UTSW HRPP/IRB**

UTSW reportable event guidance applies to all research conducted by or on behalf of UT Southwestern, its affiliates, and investigators, sites, or institutions relying on the UT Southwestern IRB. Additional reporting requirements apply for research relying on a non-UT Southwestern IRB.

According to UTSW HRPP/IRB policy, UPIRSOs are incidents, experiences, outcomes, etc. that meet **ALL three (3)** of the following criteria:

1. Unexpected in nature, frequency, or severity (i.e., generally not expected in a subject's underlying condition or not expected as a risk of the study; therefore, not included in the investigator's brochure, protocol, or informed consent document), AND
2. Probably or definitely related to participation in the research, AND
3. Suggests that the research places subjects or others at a greater risk of harm (including physical, psychological, economic, or social harm) than was previously known or recognized. Note: According to OHRP, if the adverse event is serious, it would always suggest a greater risk of harm.

For purposes of this policy, UPIRSOs include unanticipated adverse device effects (UADEs) and death or serious injury related to a humanitarian use device (HUD).

UPIRSOs must be promptly reported to the UTSW IRB within 5 working days of PI awareness.

#### For research relying on a non-UT Southwestern IRB (external, central, or single IRB):

Investigators relying on an external IRB who are conducting research on behalf of UT Southwestern or its affiliates are responsible for submitting **LOCAL** UPIRSOs to the UT Southwestern IRB within 5 working days of PI awareness. Investigators must report to their relying IRB according to the relying IRB's policy. In addition, the external IRB's responses or determinations on these local events must be submitted to the UT Southwestern IRB within 10 working days of receipt.

#### Events NOT meeting UPIRSO criteria:

Events that do NOT meet UPIRSO criteria should be tracked, evaluated, summarized, and submitted to the UTSW HRPP/IRB at continuing review.

For more information on UTSW HRPP/IRB reportable event policy, see

<https://www.utsouthwestern.edu/research/research-administration/irb/assets/policies-combined.pdf>.

---

### 7.3 Unblinding Procedures

The proposed study is not blinded.

## 8.0 DRUG/TREATMENT INFORMATION

### 8.1 **$^{68}\text{Ga}$ labelled ( $^{68}\text{Ga}$ labelled (Glu-NH-CO-NH-Lys(AHX)-HBED-CC; HBED= $N,N'$ -bis[2-hydroxy-5-(carboxyethyl)benzy]ethylenediamine- $N,N'$ -diacetic acid))**

- Other names for the drug(s):  $^{68}\text{Ga}$  PSMA-11
- Classification - type of agent: radiopharmaceutical for imaging purposes
- Mode of action: Binds to the prostate specific antigen, a cell surface protein which is over expressed in the majority of prostate cancers.
- Storage and stability: The drug solution is stored at room temperature in a gray butyl septum sealed, sterile, pyrogen-free glass vial and has an expiration time of 4 hours.
- Protocol dose: 1.8- 2.2. MBq/kg of body weight
- Preparation: Provided as unit dose by the UTSW cyclotron facility to inject into patients.  $^{68}\text{Ga}$  PSMA-11 is administered to subjects by intravenous injection. The drug solution is stored at room temperature in a gray butyl septum sealed, sterile, pyrogen-free glass vial and has an expiration time of 4 hours
- Route of administration for this study: intravenous
- Incompatibilities: none known
- Availability: Produced at the UTSW Cyclotron facility under an FDA IND
- Side effects: none known

#### 8.1.1 **Return and Retention of Study Drug**

Any unused  $^{68}\text{Ga}$  PSMA-11 will be stored at the UTSW Cyclotron Facility for up to 1 year in the event that additional testing for quality control is required.

## 9.0 CORRELATIVES/SPECIAL STUDIES

Standard of care imaging tests will be performed by the treating physician as detailed above.

Tissue obtained at the time of prostatectomy or biopsy will be reviewed for correlation with imaging tests.

## 10.0 STATISTICAL CONSIDERATIONS

---

#### **10.1 Study Design/Study Endpoints**

This is a prospective, unblended single arm, single institution phase II pilot study to explore use of  $^{68}\text{Ga}$  PSMA-11 PET/CT in aiding diagnosis of primary prostate cancer and prostate cancer metastases compared to current conventional imaging.

#### **10.2 Sample Size and Accrual**

This pilot study will generate preliminary data regarding improved diagnosis with  $^{68}\text{Ga}$  PSMA-11 to support a larger future study of using hybrid PET/MRI in diagnosis of prostate cancer.

It is anticipated that up to 20 patient will be enrolled. As this is a pilot study, nor formal sample size calculations are required.

#### **10.3 Data Analyses**

Because of the small number of subjects, descriptive statistics will be used, such as percentage of times a focus of uptake in the prostate can be seen on the PET/CT and whether this focus corresponds to any detectable abnormality on review of mp-MRI of the prostate. To be specific, we will summarize percent of incidences when 1) PET/CT is concordant with mp-MRI, 2) uptake seen on PET/CT but normal on mp-MRI and 3) no uptake on PET/CT but abnormal seen on mp-MRI. This will be displayed in a two-by-two contingency table.

Comparison will also be made to pathologic specimens from biopsy and/or prostatectomy (as reference standard) to correlate whether abnormal foci of tracer uptake correspond to sites of tumor. The per-lesion diagnostic performance of PET/CT (sensitivity and false positives) will be reported. This will be displayed in a two-by-two contingency table.

With regard to lesions outside the prostate, comparison will be made of the results from the  $^{68}\text{Ga}$  PSMA-11 scan and possible lesions seen on conventional imaging, such as pelvic CT or MRI or bone scintigraphy. To be specific, we will summarize percent of incidences when 1) PET/CT is concordant with pelvic CT/MR/BS, 2) uptake seen on PET/CT but normal on pelvic CT/MR/BS and 3) no uptake on PET/CT but lesion seen on pelvic CT/MR/BS. This will be displayed in a two-by-two contingency table.

If possible, biopsy confirmation of sites of abnormal focal  $^{68}\text{Ga}$  PSMA-11 uptake outside the prostate gland will be obtained. If biopsy is not possible due to position or size of suspected lesion, post treatment conventional imaging will be performed and results will be compared for regression in size. The per-site diagnostic performance of PET/CT (sensitivity and false positives) will be reported. This will be displayed in a two-by-two contingency table.

Agreement between two readers in continuous measurements (mean and max SUV) will be assess by intraclass correlation coefficients (ICC) and Bland-Altman plots per area of interest. Agreement between two readers in discrete measurements (visual distinguishability of primary tumor, additional primary lesion, sites of metastasis) will be assessed by Cohen's kappa.

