**STUDY SCHEMA**

## STUDY SUMMARY

Title	The Role of  Ga PSMA-11 in Enhancing Diagnosis of Primary and Metastatic Prostate Cancer
Short Title	 Ga PSMA-11 PET/CT in Prostate Cancer
Protocol Number	STU-2019-1198
Phase	Phase 2
Methodology	Unblinded single arm imaging study
Study Duration	2 years
Study Center(s)	Single-center
Objectives	To assess the ability of 68Ga PSMA-11 PET/CT to increase diagnostic accuracy in localizing primary and metastatic lesions in patients with suspected prostate cancer and elevated PI-RADS scores and PSA.
Number of Subjects	20
Diagnosis and Main Inclusion Criteria	Patients with suspected prostate cancer who have at least one PI-RADS 5 lesion, or at least one PI-RADS 4 lesion and PSA $\geq 10$ ng/mL on standard conventional imaging multiparametric MRI (mp-MRI) of the prostate and scheduled for biopsy or radical prostatectomy.
Study Product(s), Dose, Route, Regimen	 Ga Prostate Specific Membrane Antigen-11, single intravenous injection, 1.8 – 2.2 MBq/kg body weight
Duration of administration	Single intravenous administration
Reference therapy	Imaging study only
Statistical Methodology	Descriptive statistics only

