### 4.3 Imaging Analysis

For the dynamic scan, all frames will be summed to produce a single image over the pelvis. This image will be visually evaluated for focal uptake in and around the prostate gland. In addition, the dynamic image frames will also be used to construct time activity curves comparing post injection time vs standard uptake value (SUV) of  $^{68}\text{Ga}$  PSMA-11 uptake. These curves will be constructed with volumes of interest in the prostate as a whole, in any visible focal prostate lesions and over the common left iliac artery to provide an arterial input curve. If metastatic lesions are detected on this scan, separate time activity curves will be calculated as well.

Whole body images will be visually and quantitatively evaluated independently by two experienced PET/CT readers. The readers will first assess whether the primary tumor is visually distinguishable from the surrounding prostate tissue. A prostate tumor will be judged positive if the focal tracer uptake is higher than that of the surrounding prostate tissue. For calculations of SUV, a VOI will be drawn around areas of focal uptake within the prostate using iso-contour (SUVmax). The same size VOI will be drawn in the region of the uninvolved prostate. If no focal uptake is seen in the prostate, a VOI will be drawn around the prostate.

Comparisons will be made between the interpretations provided by the two PET/CT readers and the degree of agreement will be calculated. Mean and maximum SUVs will

---

be obtained on all areas of interest. Anatomic measurements of suspicious lymph nodes will be made in the short axis.

To evaluate focal uptake in lymph nodes and distant metastatic disease, VOIs will be drawn around each lesion. SUV maximum and mean will be recorded for all lesions. In addition, VOIs will be drawn around normal uptake in the prostate and a 2 cubic centimeter VOI will be drawn in the gluteal muscle, for use as normal background [7]. A lesion will be considered positive when the uptake exceeds normal background.

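### The plan neither masks PET readers to MRI lesion location nor fixes the MRI reading that decides whether a PET focus is additional

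*Combined protocol and SAP*

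**What the plan says.** Objective 2.1.1 asks whether PET/CT with early dynamic imaging finds primary lesions beyond those on mp-MRI. Section 2.4 makes per-lesion PET sensitivity the primary endpoint.

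Section 4.3 gives the reading rules:

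- Summed dynamic image: "This image will be visually evaluated for focal uptake in and around the prostate gland". No reader is named.
- Static images: "Whole body images will be visually and quantitatively evaluated independently by two experienced PET/CT readers".
- Positivity in the gland: "A prostate tumor will be judged positive if the focal tracer uptake is higher than that of the surrounding prostate tissue". No margin or SUV threshold is set.

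Sections 4.3 and 10.3 both offer, as an example statistic, "whether this focus corresponds to any detectable abnormality on review of mp-MRI of the prostate". Section 10.3 then defines three categories: concordant, PET-only and MRI-only. The PET-only category is "uptake seen on PET/CT but normal on mp-MRI". Section 10.3 also plans a kappa statistic for "Agreement between two readers in discrete measurements (visual distinguishability of primary tumor, additional primary lesion, sites of metastasis"), so an additional lesion is something each reader scores.

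On blinding, the Study Summary says "Unblinded single arm imaging study" and section 7.3 says "The proposed study is not blinded". Sections 3.1 and 4.5 make the mp-MRI a clinical scan done before entry, with at least one lesion scored 4 or 5 in every man.

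**The concern.** Two features of the reading process are left open, and each touches a main result.

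1. **What the PET reader knows.** A reader who knows where the reported MRI lesion lies can call faint uptake there positive. If that site is cancer, pathology confirms it and it counts as a PET detection. Sensitivity and concordance with MRI can both rise.
2. **How the MRI is judged.** If the MRI is re-examined with the PET focus in view, a subtle correlate may be found that the clinical report did not list. The focus then moves from PET-only to concordant, and the count that answers objective 2.1.1 falls. PET sensitivity against pathology does not change.

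The two routes act in opposite directions on PET's apparent value. A reader of the final report could not tell PET's unaided contribution from an MRI-prompted one, and the read order cannot be restored once the readers have seen the MRI.

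**Working it through.** **Text check.** The plan has no figure to reproduce: section 10.2 gives up to 20 men without a calculation, and section 10.3 is descriptive.

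- *Masking to MRI:* none stated. The independence in section 4.3 is between the two readers, since their agreement is calculated next, and it is attached to the whole-body images only.
- *Locking of the PET read:* none stated, for either image set.
- *MRI comparator:* a review is mentioned, but not who does it, when, or whether the PET is known. Every man has a reported lesion, so a normal MRI can only mean normal at that location.
- *Additional primary lesion as a reader score:* if it means beyond MRI, as in objective 2.1.1, readers need the MRI to score it. If it means a second PET focus, they do not. The plan does not say which.

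**Illustration 1: look-back and the PET-only share.** Assumed: 30 PET foci, of which 10 are absent from the MRI report. If a look-back matches a share m of those 10, the PET-only share is 10 × (1 − m) / 30.

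| m | PET-only | Share | Exact 95% interval |
|---|---|---|---|
| 0 | 10/30 | 33% | 17 to 53% |
| 0.2 | 8/30 | 27% | 12 to 46% |
| 0.3 | 7/30 | 23% | 10 to 42% |
| 0.5 | 5/30 | 17% | 6 to 35% |

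The foci are the same in every row and only the comparator changes. An interval around any one row shows sampling error but not this ambiguity. The intervals treat foci as independent, so they are too narrow if foci cluster within men.

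**Illustration 2: prompting and sensitivity.** Only cancers that PET would have missed at MRI-reported sites can be prompted. Let s be unaided sensitivity, v the MRI-reported share of confirmed lesions, and q the share of promptable misses that become calls. With misses spread evenly, the rise is q × v × (1 − s), and its ceiling is v × (1 − s).

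Assumed: 40 confirmed lesions, v = 0.5, s = 0.60. Promptable misses = 20 × 0.40 = 8.

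- q = 0: 24/40 = 60%
- q = 0.25: (24 + 2)/40 = 65%
- q = 0.5: (24 + 4)/40 = 70%
- ceiling, q = 1: (24 + 8)/40 = 80%

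The Wilson 95% interval for 28/40 is 54.6 to 81.9%, a half-width of about 13.7 points. The 10-point rise at q = 0.5 lies inside it.

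**The case against.** **The comparator wording leans towards looking at the images.** A focus with a real MRI correlate is arguably not additional to mp-MRI. This stands in part: beyond the report and beyond the images are both legitimate targets. It is therefore wrong to say that a look-back simply understates PET. The plan must still choose, and say whether the PET is known at review.

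**Added value is the stated purpose.** Section 1.4 speaks of adding PET/CT in men who already have an abnormal MRI, and section 10.2 looks ahead to hybrid PET/MRI. Reading PET with the MRI in hand is a valid add-on question. This stands, and it is why the MRI-informed read should be kept and labelled. It does not justify leaving the read order undefined.

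**Safeguards exist.** Pathology is the reference, false positives are reported, and SUVs are recorded in foci and in unaffected gland. These expose prompted calls at benign sites. They do not separate a prompted call at a true cancer from an unaided one, and no SUV threshold governs the call. Kappa does not help, because two readers with the same cue can agree more.

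**It is a small descriptive pilot without a test or decision rule.** This lowers the stakes, but the data are meant to support a larger study.

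**A stronger reading to avoid.** A reader might infer from the unblinded label that the PET readers do see the MRI, or that the reported sensitivity will be too high. The documents support neither. The label may refer only to treatment, and the text is silent on what the readers see.

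**Conclusion.** The gap is real in the supplied text, which includes no separate imaging charter. As written, the plan allows an MRI-prompted call to count towards the primary endpoint and a PET-guided look-back to reduce the PET-only category. It does not show that either will happen.

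The size and net direction are unknown. The effect on sensitivity is capped by the PET-missed cancers at MRI-reported sites: 20 points under Illustration 2, with 10 points, inside sampling error, if half are prompted. The choice of MRI comparator can halve the PET-only share, from 33% to 17%, on the assumed counts. Lesion counts, the MRI-reported share, unaided sensitivity and matching rates are all assumptions.

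The point is a low-cost improvement that should be made, held with medium confidence. It is not a flaw that invalidates the study.

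**What to change.** In sections 4.3 and 10.3:

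- (a) Read, record and lock both the summed dynamic and the whole-body PET images without access to MRI lesion location, then match. Name the reader or readers of the dynamic image. Derive additional primary lesions from the matching instead of having readers score them.
- (b) For the main table, take MRI status by location from the lesions prospectively reported on the standard-of-care mp-MRI.
- (c) Report PET-guided MRI look-back findings, and any MRI-informed PET re-read, as separate labelled counts. This also answers the added-value question for PET plus MRI.

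Optional: tabulate PET-only foci both against any reported lesion and against those scored 4 or more, and lock the PET read before pathology is known. The second option adds a scheduling burden.

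**Cost.** No added reader, scan or procedure. Section 4.2 already uses the CT to localize uptake, so a read without the MRI is workable. The MRI has to be withheld until the PET form is locked, and a located MRI lesion list has to be captured on a case report form.
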